7.3. Study Integrity

This will be a double-blind study randomized 1:1 PUL-042 Inhalation Solution: placebo.

7.4. Number of Subjects

Approximately 100 subjects (50 Pul-042 Inhalation Solution: 50 placebo) will be enrolled.

7.5. Number of Study Sites

There will be up to 15 study centers.

7.6. Duration of Subject Participation

Subjects will participate for approximately 28 days.

7.7. Schedule of Study Activities

The schedule of events is presented in [Table 1](#).

Table 1: Schedule of Events

Event	Screening	Dose 1 ^{a,b}	Dose 2, 3 ^a	Follow-up	Follow-up/Early Discontinuation from Study	Study End
	V1	V2	V3, 4	V5	V6	V7
	Day -2 to Day 1	Day 1 ^b	Days 3, 6	Day 10	Day 15	Day 29
Informed consent	X					
Medical history	X					
Pregnancy test ^c	X				X	X
Physical exam	X	X	X	X	X	
Vital signs ^d	X	X	X	X	X	
Pulse oximetry	X					
Spirometry ^e	X	X	X			
Symptom Score	X	X	X	X	X	X
SARS-CoV-2 test ^f	X				X	X
Ordinal Scale for Clinical Improvement	X	X	X	X	X	X
Study drug administration ^g		X	X			
Adverse events	X	X	X	X	X	X
Concomitant medications	X	X	X	X	X	X
Randomization	X					

^a Vital signs, adverse events, and concomitant medications will be assessed prior to administration of study medication and also at 30 minutes post-dose.

^b There is no Day 0 in this study

^c Urine pregnancy test or serum pregnancy test if women are of child-bearing potential. If urine pregnancy test is positive, a serum pregnancy test must be done. Pregnancy test will be repeated at Day 29 or Early Discontinuation

^d Vital signs will include body temperature, blood pressure measurements, heart rate, and respiratory rate

^e Spirometry will be done at screening to document eligibility. On days of dosing, spirometry will be done pre-dose and at 30 minutes (± 15) minutes post-dose. If the FEV1 is reduced $> 10\%$ compared to the pre-dose baseline the FEV1 should be repeated as clinically indicated

^f SARS-CoV-2 testing will be performed at screening to confirm eligibility if a positive test SARS-CoV-2 has not been documented. SARS-CoV-2 testing will be performed at Early Discontinuation visit

^g Study drug administration must be done by a health care professional

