A similar potential pharmacodynamic effect was seen in the spirometry data (specifically the forced expiratory volume in 1 second [FEV1]) from PUL-042-001, likely due to the effect of PUL-042 on the bronchial airways. A dose-dependent decrease in FEV1 was seen with a nadir at approximately 30 minutes post-dose in subjects treated with PUL-042 Inhalation Solution. There was no comparable decline observed with placebo. These measurements were largely within the 12% change from baseline accepted as normal variability. This was followed by a recovery to near baseline levels at 24 hours post dose. Over the course of 7 days, the mean FEV1 was within 0-5% of the baseline value, with the subjects who received higher doses of PUL-042 showing a larger mean decrease in FEV1. None of the decreases in FEV1 were accompanied by signs of respiratory distress or a drop in oxygen saturation. None of the FEV1 results in the PUL-042 inhalation treated groups were statistically different from placebo after the 30-minute time point. The MTD delivered as a single dose was established as 40.6 µg Pam2 : 59.5 µg ODN in PUL-042-001.

A second phase 1 study (PUL-042-003) has been completed. PUL-042-003 was a randomized, open-label, cross-over study to determine the safety and tolerability of PUL-042 Inhalation Solution and to explore the effect of pretreatment with either cromolyn sodium or albuterol sulfate. The primary objective of this study was to determine the safety and tolerability in healthy normal subjects of single or repeated doses of PUL-042 in SWFI. Exploratory objectives include determining whether ANC was an indicator of biological activity and to determine 1) the duration of local biological activity in the bronchial airways by serial FEV1 measurements, 2) whether the administration of cromolyn sodium prior to the administration of PUL-042 had an effect on the FEV1 response, and 3) whether the administration of albuterol prior to the administration of PUL-042 had an effect on the FEV1 response.

In protocol PUL-042-003, the first cohort of 8 subjects (cohort 1) received a dose of 20.3 µg Pam2 : 29.8 µg ODN (1/2 the single-dose MTD of PUL-042) with or without pretreatment with cromolyn sodium (4 each). Subjects were then crossed over to the alternative treatment after a 2-week follow-up period and an additional 2-week washout period.

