7.2. Subject Selection

7.2.1. Inclusion Criteria

Subjects aged 18 years or older must fulfill all of the following inclusion criteria to be eligible for the study:

1. Subjects must have a positive test for SARS-CoV-2.
2. COVID-19 signs and symptoms such as (fever, cough, shortness of breath or fatigue) with onset within the 7 days prior to Screening and/or within 9 days of the first dose administered on Day 1
3. Subjects should be Ordinal Scale for Clinical Improvement score of 4 or less
4. Subjects receiving oxygen should have pulse oximetry $\geq 93\%$ on 3 liters per minute of oxygen or less delivered by nasal prongs
5. Subjects can be receiving standard of care (SOC) for COVID-19, this includes marketed therapies or therapies with Emergency Use Authorization (EUA) for COVID-19 treatment.
6. Subject's spirometry (FEV₁ and forced vital capacity [FVC]) must be $\geq 70\%$ of predicted value.

7. If female, the subject must be surgically sterile or \geq 1 year postmenopausal. If of child-bearing potential (including being $<$ 1 years postmenopausal) and, if participating in sexual activity that may lead to pregnancy, the subject agrees to use an effective dual method of birth control (acceptable methods include intrauterine device, spermicide, barrier, male partner surgical sterilization, and hormonal contraception) during the study and through 30 days after completion of the study.
8. If female, must not be pregnant, plan to become pregnant, or nurse a child during the study and through 30 days after completion of the study. A pregnancy test must be negative at the Screening Visit, prior to dosing on Day 1.
9. If male, must be surgically sterile or, if not surgically sterile and if participating in sexual activities that may lead to pregnancy, be willing to practice two effective methods of birth control (acceptable methods include barrier, spermicide, or female partner surgical sterilization) during the study and through 30 days after completion of the study.
10. Must have the ability to understand and give informed consent.

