7.2.2. Exclusion Criteria

Subjects will be excluded if they fulfill any of the following exclusion criteria:

1. No documented infection with SARS-CoV-2.
2. Patients who are in respiratory distress or require high flow oxygen, non-invasive ventilation or mechanical ventilation (Ordinal Scale for Clinical Improvement $>$ 4) or with pulse oximetry less than 93% on oxygen with a flow rate of 3 liters per minute or less by nasal prongs at the time of screening.
3. Known history of chronic pulmonary disease (e.g., asthma [including atopic asthma, exercise-induced asthma, or asthma triggered by respiratory infection], chronic pulmonary disease, pulmonary fibrosis, COPD), pulmonary hypertension, or heart failure.
4. Exposure to any investigational therapy (defined as any agent not currently marketed or without EUA) at the time of or within 30 days prior to the Screening Visit.
5. Any condition which, in the opinion of the Principal Investigator, would prevent full participation in this trial or would interfere with the evaluation of the trial endpoints.

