7.11.2. Days 3 and 6 (Study Drug Administration)

Dosing

PUL-042 administration must be supervised by a health care professional. PUL-042 will be administered via a PARI Sprint nebulizer equiped with a filter valve to prevent aerosol generation. A nose clip will be used during the nebulization procedure. All doses will be administered as a constant volume (4 mL) via nebulization; the nebulizer will be operated until all drug has been delivered. All of the following time points are defined relative to the completion of dosing (T_0).

Note: Missed doses should not be replaced

Post-Dose Guidelines

In previous studies with healthy volunteers, some subjects have demonstrated a transient decrease in lung function, usually asymptomatic. To date, subjects have recovered to at or near baseline lung function values without the administration of rescue medication. However, if after administration of PUL-042 Inhalation Solution there are clinical symptoms of decreased lung function, albuterol (salbutamol) can be administered.

Following dosing, if a reduction of FEV1 $>10\%$ relative to pre-treatment is recorded, the patient should have the FEV1 measurement repeated as clinically indicated. If a reduction of FEV1 $>12\%$ relative to pre-treatment is recorded at 4 hours, the patient must be reviewed by the Principal Investigator prior to further dosing. If a reduction of FEV1 $>12\%$ persists for up to 4 hours and is associated with clinical symptoms over this period, no further investigational treatment should be administered. Albuterol (salbutamol) may be given to symptomatic patients at the discretion of the investigator.

If a reduction of FEV1 >20% relative to pre-treatment is recorded, no further investigational treatment should be administered to that patient. Patients whose COVID-19 condition deteriorates such that they can no longer be given treatment by nebulization or require mechanical ventilation will be discontinued from further dosing.

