8.3. Physical Examination and Vital Signs

A qualified medical person will perform a physical examination at all indicated visits.

- Physical examination: general appearance, head, eyes, ears, nose, throat, neck, cardiovascular, lungs, abdomen, lymph nodes, extremities, neurological, skin, musculoskeletal, and other.
- Vital signs will include body temperature, blood pressure, heart rate, and respiratory rate.

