13.3. Primary Objective

To determine the efficacy of PUL-042 Inhalation Solution in decreasing the severity of COVID-19 in subjects: 1) who have documented SARS-CoV-2 infection, and 2) if receiving oxygen, should have pulse oximetry $\geq 93\%$ on 3 liters per minute of oxygen or less delivered by nasal prongs (Ordinal Scale for Clinical Improvement 4 or less) at the time of enrollment.

The primary endpoint for this study will be the difference in the proportion of patients with clinically meaningful worsening of COVID-19 within 28 days from the start of experimental therapy, as indicated by an increase of at least 2 points on the Ordinal Scale for Clinical Improvement.

The Ordinal Scale for Clinical Improvement is a 9-point scale that measures disease severity. For this study, an increase of 2 or more points is considered meaningful worsening of disease ([Table 4](#)). This endpoint considers changes in disease severity that are observed at any time over the course of this study.

This endpoint will be evaluated as the difference in binomial proportions under the null hypothesis of no difference between randomized treatment groups. Full details of the planned analysis will be included in the Statistical Analysis Plan that will be developed for this study.

The Ordinal Scale for Clinical Improvement to be used in this study is derived from a draft scale proposed by the World Health Organization⁹ for clinical improvement as presented below:

Table 4: Ordinal Scale for Clinical Improvement (Derived from draft WHO scale)⁹

Descriptor	Score
No clinical or virological evidence of infection	0
Infected but no limitation of activities	1
Limitation of activities	2
Hospitalized not requiring oxygen therapy (SpO ₂ > 93% on room air)	3
Oxygen by mask or nasal prongs	4
Non-invasive ventilation or high-flow oxygen	5
Intubation and mechanical ventilation	6
Ventilation + additional organ support- pressors, RRT, ECMO	7
Death	8

It is possible that medically justified treatment and or procedures cannot be implemented due to the unavailability of equipment (e.g., scarcity of ventilators). In such cases, the data recorded in the eCRF should reflect the prescribed circumstances rather than the reality. For example, if clinical evaluation of a patient indicates the need for mechanical ventilation when no ventilator is available, that patient should be scored as 6 – “Intubation and mechanical ventilation” not as a lower score on the Ordinal Scale for Clinical Improvement.

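### Pulse oximetry is scheduled only at Screening, so oxygen saturation is not systematically measured after any dose, on Days 3 or 6, or at follow-up

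*Protocol*

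**What the plan says.** **Schedule.** In Protocol 7.7, Table 1, the row "Pulse oximetry" has one mark, under Screening. SAP Appendix A is the same. Among the visit lists in Protocol 7.9 to 7.15, only the Screening list (7.9) names oximetry.

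**Vital signs.** Table 1 footnote d reads "Vital signs will include body temperature, blood pressure measurements, heart rate, and respiratory rate". Protocol 8.3 agrees: "Vital signs will include body temperature, blood pressure, heart rate, and respiratory rate". SAP 7.4 summarizes blood pressure, pulse, respiratory rate and temperature.

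**Prior saturation data.** Protocol 5.4 describes a dose-dependent FEV1 fall, lowest about 30 minutes after dosing, and adds: "None of the decreases in FEV1 were accompanied by signs of respiratory distress or a drop in oxygen saturation". Both studies for which it reports this (PUL-042-001 and -003) were in healthy subjects.

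**Population.** Protocol 7.2.1 admits subjects on oxygen if saturation is at least 93% "on 3 liters per minute of oxygen or less delivered by nasal prongs". Protocol 7.2.2 item 2 excludes "Patients who are in respiratory distress or require high flow oxygen, non-invasive ventilation or mechanical ventilation", judged at screening.

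**Stopping of dosing.** Protocol 7.10.2 and 7.11.2 use FEV1 and symptom criteria, and add that patients who deteriorate so that "they can no longer be given treatment by nebulization or require mechanical ventilation will be discontinued from further dosing". For Days 3 and 6, 7.11.1 also lets the investigator hold or stop dosing for safety or deterioration.

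**Analysis.** SAP 5.4 lists oximetry as a baseline characteristic, if available. SAP 7 names adverse events, vital signs and pulmonary function tests as the safety assessments. The ongoing safety review in Protocol 13.5 does not list saturation either.

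**The concern.** The trial repeats spirometry at the time when the FEV1 effect is expected to be greatest, but schedules no saturation reading beside it. Protocol 5.4 relies partly on the absence of desaturation, as seen in healthy volunteers. Whether that carries over to patients with COVID-19, some already on oxygen, is a natural safety question for a Phase 2 study. The plan as scheduled cannot answer it by arm, and the DSMB would have no planned saturation data at its reviews after 20, 40 and 60 subjects.

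The other routes by which a fall in saturation might surface are weak. The Ordinal Scale is scored before dosing but not at 30 minutes, so it would miss a transient fall. Adverse events are assessed at 30 minutes, but Protocol 12 and 12.4 say that events associated with SARS-CoV-2 infection are to be scored on the scales and not reported as adverse events. Desaturation in these patients is easily put down to COVID-19.

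**Working it through.** No power, alpha or event figure is involved. The check is a reading of the schedule and a count of days and readings.

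**1. Where saturation is scheduled**

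| Time point | Source | Oximetry | Vital signs |
|---|---|---|---|
| Screening, Day -2 to Day 1 | Protocol 7.9 | yes | yes |
| Day 1 pre-dose | 7.10.1 | no | yes |
| Day 1, 30 min post-dose | 7.10.3 | no | yes |
| Days 3 and 6 pre-dose | 7.11.1 | no | yes |
| Days 3 and 6, 30 min post-dose | 7.11.3 | no | yes |
| Day 10 | 7.12 | no | yes |
| Day 15 | 7.13 | no | yes |
| Early withdrawal | 7.14 | no | yes |
| Day 29 | 7.15 | no | no |

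Protocol 7.10.1 says that Screening assessments need not be repeated if done on Day 1. A subject screened that day therefore has one pre-dose reading on a dosing day.

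**2. Age of the only reading at each dose.** Inputs: Screening on Day -2 to Day 1, no Day 0, and Days 3 and 6 each with a window of 1 day either side (7.11). The shortest interval starts from Day 1 and the longest from Day -2.

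- Dose 1 (Day 1): 0 to 2 days.
- Dose 2 (Day 2 to Day 4): Day 1 to Day 2 = 1 day; Day -2 to Day 4 = 5 days.
- Dose 3 (Day 5 to Day 7): Day 1 to Day 5 = 4 days; Day -2 to Day 7 = 8 days.

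**3. Dosing-related readings not scheduled**, assuming 100 subjects who all receive three doses:

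- Post-dose: 3 doses × 1 reading = 3 per subject; 3 × 100 = 300.
- Pre-dose: 3 per subject, or 2 if Screening falls on Day 1; 200 to 300 over 100 subjects.
- Total: 5 to 6 per subject; 500 to 600 over 100 subjects.

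The 300 post-dose readings are absent whenever Screening takes place. Subjects who stop dosing early reduce the totals.

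**4. Entry limits beside dosing rules.** High-flow oxygen and non-invasive ventilation exclude a subject at entry (7.2.2 item 2) and correspond to score 5 in Protocol Table 4. After randomization, apart from the FEV1 criteria, 7.10.2 and 7.11.2 require discontinuation only for inability to nebulize or mechanical ventilation. A subject who reaches score 5 by Day 3 or 6 but can still be nebulized is left to the discretion given in 7.11.1.

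**The case against.** The best defence is that the plan already watches the airway effect closely. Respiratory rate, spirometry and adverse events are assessed 30 minutes after each dose. There are graded FEV1 actions above 10%, 12% and 20%, and a health care professional supervises dosing. Entry requires FEV1 and FVC of at least 70% of predicted and excludes chronic lung disease. Protocol 5.4 also relies on spontaneous recovery of FEV1 and on changes largely within normal variability. It reports no apparent safety concern in the ongoing rhinovirus-challenge study, which is still blinded and for which saturation is not mentioned. No planned endpoint uses post-baseline saturation, so no analysis fails for lack of it. All of this stands and limits the seriousness of the point. None of it measures saturation after a dose.

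A reader might infer more than the documents support:

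- **That saturation is never measured on a dosing day.** This is true of Days 3 and 6. On Day 1 it depends on when Screening takes place.
- **That the 93% limit decides each dose, so that the dosing rules rest on a variable not collected.** The limit is an entry criterion for subjects receiving oxygen. The Day 3 and 6 rules use FEV1, symptoms, discretion, ability to nebulize and mechanical ventilation, none of which needs an oximeter.
- **That the entry and discontinuation texts contradict each other.** They answer different questions and differ for score 5. That score is defined by the support given, and the scale is scored before each dose, so it would be visible.
- **That the primary endpoint is misclassified.** Score 3, "Hospitalized not requiring oxygen therapy", carries a saturation condition in parentheses, but the boundary with score 4 is whether oxygen is given. Protocol 14.7 also requires eCRF entries to be supported by medical records, so a missing schedule row does not show that source data are absent.
- **That desaturation would go wholly unrecorded.** A detected event could be reported as an adverse event, subject to the COVID-19 exclusion described above.

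**Conclusion.** The point holds as a gap in safety measurement. After Screening, no saturation reading is scheduled at any visit, and none follows any of the three doses. By the third dose, the only scheduled reading is 4 to 8 days old. The 500 to 600 absent readings assume 100 subjects who all receive three doses. The range depends on how many are screened on Day 1, which the documents do not give. It counts readings not taken. It does not estimate missed desaturations, bias or loss of power, for which the documents give no basis.

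The efficacy analysis is unaffected. The change is worth making because the FEV1 effect is known, the reassurance about saturation comes from a different population, and readings not taken during the trial cannot be recovered. The handling of score 5 after randomization is a separate matter of reconciling text, which added oximetry would not settle.

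**What to change.** Add SpO2, with the oxygen flow at the time, to the vital-signs definition in Protocol Table 1 footnote d, Protocol 8.3 and SAP 7.4, and carry the change into SAP Appendix A. Because vital signs are already taken at those points, this gives a reading pre-dose and 30 minutes post-dose on Days 1, 3 and 6, at Days 10 and 15, and at early withdrawal. It does not reach Day 29, where no vital signs are scheduled; if a reading is wanted there, it needs its own entry in Table 1 and 7.15.

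In SAP 7.4, add a descriptive summary by arm of the pre- to post-dose change on each dosing day, and include it in the DSMB outputs.

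The cost is a few eCRF fields and one descriptive table, using the kind of device already needed at Screening, with no new visit or staff.

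Separately, the sponsor should reconcile Protocol 7.2.2 item 2 with 7.10.2 and 7.11.2 for subjects who reach score 5 after randomization. Which rule applies is for the sponsor to decide; no threshold or dosing rule is proposed here.

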7.8. Subject Participation

Subjects will be followed for the duration of the entire study (28 days) to assess the severity of COVID-19. The following are general guidelines for study conduct:

- Subjects should complete all visits as outlined in the protocol.
- Patients in whom dosing is discontinued for any reason should continue to be followed according to the visit schedule.

7.9. Study Day -2 to Day 1 (Screening)

The following assessments will be conducted prior to performing any study-specific procedures:

- Informed consent: The subject will sign an informed consent form approved by the governing Institutional Review Board (IRB) or Ethics Committee.

Once the informed consent is obtained, the following will be conducted as part of Screening to document subject eligibility for the study.

- Medical history (including documentation of SARS-CoV-2 infection and date of onset of symptoms of SARS-CoV-2 infection)
- Physical examination (including height and weight)
- Serum pregnancy test or urine test (if urine test is positive, a serum test must be conducted)
- Vital signs
- Pulse oximetry
- Spirometry
- Nasopharyngeal or oropharyngeal sample for SARS-CoV-2 testing if a positive test for SARS-CoV-2 has not been documented
- SARS-CoV-2 infection symptom score
- Ordinal Scale for Clinical Improvement assessment
- Concomitant medication assessment
- Randomization to study treatment
- Adverse event (AE) assessment (AE collection starts at the time the time of randomization to study treatment and is continuous throughout the study until 28 days after receiving study drug)

7.10. Study Day 1

7.10.1. Day 1 (Pre-dose)

Assessments conducted during Screening do not have to be repeated if done on Day 1.

The following should be obtained prior to dosing.

- Physical examination
- Vital signs
- Spirometry
- SARS- CoV-2 infection symptom score
- Ordinal Scale for Clinical Improvement assessment
- Adverse event assessment
- Concomitant medication assessment

7.10.3. Day 1 ($T_0 +30$ minutes [± 15 minutes])

- Vital signs
- Spirometry
- Adverse event assessment

- Concomitant medication assessment

